3.2 SECONDARY MEASURED OUTCOMES

The following outcomes will be measured:

- The proportion of subjects with neurological death or ipsilateral stroke within the first 30 days following completion of all PHIL treatments
- Angiographic occlusion of the pre-specified target vessel intended for treatment at procedure following completion of all PHIL treatments
- New-onset or worsening of permanent morbidity at 6 month follow-up
- New-onset intracranial hemorrhage at 6 month follow-up
- New-onset of cranial nerve palsy at 6 month follow-up
- Clinically significant technical events during the PHIL embolization procedure(s) including but not limited to reflux of embolic material, migration of the embolic material, catheter entrapment or damage, and vessel dissection.
- Device-related adverse events at procedure and 30 days
- Device-related mortality at procedure and 30 days
- Procedure related adverse events including complications of arterial puncture, contrast-induced nephropathy, radiation-induced injuries, renal and anesthesia-related complications.

New-onset of device- or procedure-related neurological deficit or adverse event, or worsening of a previous neurological complaint, disorder, deficit, or adverse event that is unresolved at 6 month follow-up even if not associated with a change in mRS.Permanent morbidity is defined as a worsening of mRS score at 6 month follow-up compared to the baseline mRS score of:

- ≥1 point in subjects experiencing a stroke
- ≥2 points in subjects experiencing neurological adverse events.

Note, worsening mRS scores associated with non-neurological causes, resulting in limitations to the subject's ability to walk or require assistance to attend to own bodily needs, will not be considered permanent morbidity. This includes medical events such as, bone fractures, muscle, ligament and tendon injuries, and other physical injuries.

3.3 Additional measured outcomes

The following outcomes will be measured:

- Improvement of neurological symptoms
- Number of procedures required to treat the fistula at 6 months follow-up
- Procedure time (defined as first to last fluoroscopic or digital subtraction angiographic acquisitions)
- Radiation exposure (dosage and time)
- Injected volume of PHIL
- Modified Rankin Scale (mRS) at 3 and 6 months
- Self-reported QOL questionnaire, EQ-5D at 6 months
- Unplanned adjunctive treatments

3.4 Type / Design of the study

The proposed study is a prospective, multicenter, single-arm, open label clinical study to assess the safety and probable benefits of PHIL® device for the treatment of intracranial dural arteriovenous fistulas (dAVF). The design is depicted in Figure 2.

[figure not shown]

FIGURE 2 SCHEMATIC DIAGRAM OF TRIAL DESIGN

3.5 Measures to minimize bias

A screening log serves as a method for the Sponsor to ensure that there is no selection bias in the trial.

3.6 Medical device information

The PHIL Liquid Embolic Material agent is indicated in the treatment of intracranial dural arteriovenous fistulas.

The PHIL® device is a non-adhesive liquid embolic agent comprised of a Triiodophenol-(lactide-co-glycolide) acrylate and hydroxyethyl methacrylate (HEMA) co-polymer dissolved in DMSO (dimethyl sulfoxide). An iodine component is chemically bonded to the co-polymer to provide a radio pacifier element during fluoroscopic visualization. The PHIL® Liquid Embolic System consists of a sterile, pre-filled, 1.0 mL syringe of PHIL® liquid embolic, a sterile, pre-filled 1.0 mL syringe of DMSO, and microcatheter hub adaptors. A DMSO compatible delivery microcatheter that is indicated for use in the neurovascular or peripheral vasculature is used to access the embolization target site. The PHIL® Liquid Embolic System is available in several product formulations: PHIL® 25%, PHIL® 30%, and PHIL® 35%. PHIL® 25% liquid embolic will travel more distally and penetrate deeper into the nidus due to its lower viscosity

compared to PHIL® 30% or 35% liquid embolic. Final solidification occurs within three minutes for all product formulations.

The PHIL® device is delivered by slow, controlled injection through a microcatheter into the vascular malformation under fluoroscopic control. The DMSO solvent dissipates into the blood, causing the co-polymer to precipitate in situ into a coherent embolus. The PHIL® device immediately forms a skin as the polymeric embolus solidifies from the outside to the inside, while traveling more distally in the vascular lesion.

3.6.1 DEVICE LABELING

The PHIL device is considered investigational in this study and is required to be used per the protocol and as specified in the Investigational Device Exemption (IDE) Instructions for Use (IFU) document. The IDE IFU is provided separately to each investigator.

3.6.2 Device accountability procedures

U.S. Federal law requires that all investigational medical devices be strictly controlled. All study devices must be kept in a secured area at the clinical sites in compliance with all applicable FDA regulations.

The Principal Investigator or designated study site personnel must verify the receipt of the study devices. Device disposition must be documented.

For applicable sites, at the end of enrollment in the study, all test devices and device accessories provided by the Sponsor will be returned to the Sponsor. Problematic devices and products, including all components, should be returned to the Sponsor or its designee for investigation.

3.6.3 DEVICES AND EQUIPMENT

In addition to the PHIL device, devices that may be required for the study procedure include (but are not limited to) those listed below.

- Access devices: Guiding catheter and sheath
- Delivery catheters: Microcatheters
- Non-ionic contrast
- Guidewires
- Any other adjunctive, approved/cleared device for dAVF treatment

The placement procedure is described in detail in the Instructions For Use (IFU) document. The Investigator should review and understand the complete IDE IFU prior to performing any PHIL device placement in this clinical study.

It is recommended that DMSO-compatible microcatheters be used during the study procedure. At present, the following MicroVention microcatheters are DMSO-compatible: Headway® DUO, Headway® 17 and Scepter Occlusion Balloon microcatheter.

Should additional DMSO-compatible microcatheters become available during the course of this study, they may also be used for the study procedure.

3.7 EXPECTED SUBJECT DURATION

Study participation includes initial screening, consent, index procedure, post-procedure, hospital discharge, any supplemental embolization procedures and return for follow-up visits at 30 days post-procedure (following

completion of treatment of dAVF embolization with PHIL) and at 6 months post-procedure (following completion of treatment of dAVF embolization with PHIL).

The total subject duration is expected to be approximately 9 months.

4 SELECTION AND WITHDRAWAL OF SUBJECTS

Subjects who are enrolled in the study but subsequently do not meet the pre-operative inclusion criteria below will not be treated with the PHIL and will be considered enrolled but not treated. These subjects will be considered screen failures, exited from the study, replaced with other subjects that satisfy enrollment and pre-procedural inclusion criteria and will not be included in the analyzed populations.

Before any subject is treated in the study, the screening / baseline angiogram will be reviewed by at least one of the Study Principal Investigators.

4.1 INCLUSION CRITERIA

To be enrolled in this study subjects must meet ALL of the following criteria:

- 1) Subject is ≥22 and ≤80 years of age.
- 2) Subject is willing and capable of complying with all study protocol requirements, including specified follow-up period.
- 3) Subject or authorized legal representative must sign and date an IRB approved written informed consent prior to initiation of any study procedures.
- 4) Subject has an intracranial dAVF that can be treated by embolization with PHIL without the need for other liquid embolization products (e.g., Onyx, nBCA).
- 5) Subject has an intracranial dAVF that is deemed appropriate for embolization with PHIL without significantly increased risk to collateral or adjacent territories.

4.2 GENERAL EXCLUSION CRITERIA

Subjects shall be excluded from the study if ANY of the following conditions exist:

- 1) Subject has a modified Rankin Scale of >3 or has another neurological deficit not due to stroke that may confound the neurological assessments.
- 2) Subject having multiple dAVFs to be treated
- 3) Subject has dAVF requiring pre-planned treatment with adjunctive treatments (i.e. embolic coils, surgical resection, etc).
- 4) Subject presents with an intracranial mass or is currently undergoing radiation therapy for carcinoma or sarcoma of the head or neck region
- 5) Subject has known allergies to DMSO (dimethyl sulfoxide), iodine or heparin
- 6) Subject with a history of life threatening allergy to contrast media (unless treatment for allergy is tolerated)
- 7) Subject is experiencing (or has experienced) an evolving, acute, or recent disabling ischemic stroke, has conditions placing them at high risk for ischemic stroke or has exhibited ischemic symptoms such as transient ischemic attacks, minor strokes, or stroke-in-evolution within the prior 3 months timeframe.
- 8) Subject has had an acute myocardial infarction within 30 days prior to index procedure
- 9) Subject has had or plans to have any major surgical procedure (i.e. intra-abdominal or intrathoracic surgery or any surgery/interventional procedure involving cardiac or vascular system) within 30 days of the index procedure

- 10) Subject is currently participating in another clinical study which may interfere with outcome measurements for this study
- 11) Female subject is currently pregnant.
- 12) Subject has an acute or chronic life-threatening illness other than the neurological disease to be treated in this study including but not limited to any malignancy or debilitating autoimmune disease
- 13) Subject has existing severe or advanced comorbid conditions which significantly increase general anesthesia and/ or surgical risk including but not limited to advanced COPD, uncontrolled hypertension / diabetes, congestive heart failure, chronic or acute kidney disease.
- 14) Subject has evidence of active infection at the time of treatment
- 15) Subject has dementia or cognitive or psychiatric problem that prevents the patient from completing required follow-up.
- 16) Subject has co-morbid conditions that may limit survival to less than 24 months.
- 17) Subject has a history of bleeding diathesis or coagulopathy, international normalized ratio (INR) greater than 1.5, or will refuse blood transfusions.

4.3 Angiographic exclusion criterion

- 1) Subject has severe calcification or vascular tortuosity that may preclude the safe introduction of the sheath, guiding catheter, or access to the lesion with the microcatheter.
- 2) Subject has a contra-indication to DSA, CT scan or MRI/ MRA.
- 3) Subject has a history of intracranial vasospasm not responsive to medical therapy.
- 4) Subject has extra-cranial stenosis or parent vessel stenosis > 50% proximal to the target lesion to be treated.

4.4 Participant withdrawal or study termination

Subjects may withdraw from the study at any time without penalty or loss of medical care, or they may be withdrawn at any time at the discretion of the PI for safety or administrative reasons. The Sponsor may terminate or suspend the study at any time.

4.4.1 SUBJECT WITHDRAWAL

All enrolled subjects have the right to withdraw their consent at any time during this study. All data collected until the time of subject withdrawal will remain in the study database and will be used for analysis. Whenever possible, the site staff should obtain written documentation from the subject who wishes to withdraw his/her consent for future follow-up visits. If the site staff is unable to obtain written documentation, all information regarding the subject's withdrawal must be recorded in the subject's medical record. In addition, the appropriate eCRFs must be completed for the subject and clear documentation of the subject's withdrawal should be provided to the Sponsor.

4.4.2 Subject discontinuation by investigator

An Investigator may discontinue a subject from the study, with or without the subject's consent, for any reason that may, in the Investigator's opinion, negatively affect the well-being of the subject. If a subject is withdrawn from the study, the Investigator will promptly inform the subject and Sponsor.

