7.1 PROCEDURE FOR ADVERSE EVENT REPORTING

Any medical condition that is present at the time that the subject is screened will be considered part of the subject's baseline medical history and not reported as an adverse event. However, if the subject's condition deteriorates at any time during the study, it may be recorded as an AE. Adverse events will be collected from the point of enrollment in the study until a subject exits the study.

Information to be collected includes event description, time of onset, clinician's assessment of severity, relationship to study product (assessed only by those with the training and authority to make a diagnosis), and time of resolution/stabilization of the event. AEs will be categorized using the definitions in Section 7.2. All AEs collected during the study must be followed by the Investigator until resolution or until the end of the 6 month follow-up. All applicable AEs occurring while on study must be documented appropriately regardless of the relationship.

A list of potential anticipated adverse events is provided in Section 1.3.2. AE reporting responsibilities are described in Section 7.2.

Changes in the severity of an AE will be documented to allow an assessment of the duration of the event at each level of severity to be performed.

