7.3 Adverse event follow-up

Subjects experiencing an adverse event will be followed as per standard medical care. Data collection will be ongoing for the subject's duration in the clinical study as defined in follow-up period described in Section 5.

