11.8.4 Study discontinuation by sponsor

The Sponsor may choose to discontinue the study should the Sponsor discover additional information during the study that may cause harm to subject safety.

If the study is terminated prematurely or suspended, the Sponsor will promptly inform all clinical Investigators of the termination or suspension and the reason(s) for this. The IRB/EC will also be informed, either by the Sponsor or Investigator if a local IRB/EC is utilized, promptly and provided with the reasons(s) for the termination. If applicable, regulatory authorities will be informed. Enrolled subjects will be asked to complete all remaining study visits and the subject will then be seen by the treating physician per standard clinical care following dAVF treatment.

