## 8.6 Handling of Missing Data

If there is missing data in primary and secondary outcome, sensitivity analysis will be performed on the imputed data.

Subjects whose data are not missing at random, such as those who exit the study due to a device-related primary safety event, will be considered a failure for the probable benefit endpoint and will be considered to have a primary safety event for the primary safety endpoint.

Subjects with missing data who exit the study due to a non-device-related primary safety event will be imputed by the multiple imputation methods; similarly, their missing probable benefit endpoint will also be imputed by the multiple imputation methods.

Subjects who are absent at post-procedure visits and can be assumed to be missing at random, will have their success or failure imputed for the primary safety and probable benefit endpoints. For example, if a study stops follow-up for reasons other than a device-related primary safety event, that subject will be imputed by the methods discussed below.

For multiple imputation methods, the assumption is that data from subjects undergoing imputation is missing at random (Little and Rubin (2000)). A comprehensive sensitivity analyses called the tipping point analysis will be done. In this analysis, one can start with either the worst-case analysis in which all missing at random data will be assigned a failure for the primary endpoint, or can be started with the best case scenario in which all missing at random subjects will be assigned a success for the primary endpoint. The tipping point analysis provides result for all possible outcomes from the imputation process and is thus comprehensive.

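### Data collection ends when the investigator removes a treated subject from the study, which leaves the 6-month secondary safety outcomes open to informative missingness

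*Protocol*

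**What the plan says.** **Removal.** Protocol 4.4 says of subjects that "they may be withdrawn at any time at the discretion of the PI for safety or administrative reasons". Protocol 4.4.2 says "An Investigator may discontinue a subject from the study", whether or not the subject agrees, for any reason that could "negatively affect the well-being of the subject" in the investigator's opinion. The only stated follow-on step is to tell the subject and the sponsor promptly.

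**Data after exit.** Protocol 7.1 says "Adverse events will be collected from the point of enrollment in the study until a subject exits the study". Protocol 7.3 says "Data collection will be ongoing for the subject's duration in the clinical study". Protocol 7.1 also says "All AEs collected during the study must be followed by the Investigator until resolution or until the end of the 6 month follow-up".

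**Contrast.** If the sponsor stops the whole study, Protocol 11.8.4 says "Enrolled subjects will be asked to complete all remaining study visits".

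**Analysis.** SAP 8.3 reports each secondary outcome as a count and percentage of the subjects evaluated, with Clopper-Pearson limits. SAP 8.6 treats as not missing at random those subjects "such as those who exit the study due to a device-related primary safety event", and counts them as safety events and benefit failures.

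**The concern.** Protocol 4.4.2 ties removal to the subject's well-being, and 4.4 lists safety among its grounds. Such removals are plausibly related to the outcomes that the study is meant to measure. After removal, the documents request no visit, telephone contact, mRS or vital-status check.

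Permanent morbidity is defined by the change in mRS from baseline to 6 months. A removed subject has no 6-month score and cannot be classified. A hemorrhage or cranial nerve palsy that begins after exit is not collected. If removed subjects do worse than those who stay, the 6-month rates come out too low. The SAP also plans comparison with published rates where applicable (SAP 8.1), so an understated rate could carry into that comparison.

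**Working it through.** **1. The plan's own figure.** Protocol 8.1 and SAP 6 enroll up to 75 subjects to obtain 6-month follow-up in 60, allowing 15 losses.
- 15/75 = 20%, and 60/(1 − 0.20) = 75. The figure reproduces.
- The 15 are losses to follow-up, which Protocol 4.4.3 defines as subjects not reached after three attempts. They are not an allowance for investigator removals. No figure for removals is given.

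**2. What is collected after an investigator removal.**
- New adverse events: not collected (Protocol 7.1, enrollment to exit).
- Events already recorded: unclear. One sentence of 7.1 requires follow-up to resolution or to the end of the 6-month period. Another ends collection at exit, and 7.3 limits data collection to the subject's time in the study.
- 6-month mRS: not requested.
- Vital status: not requested.
- Reason for exit: reported to the sponsor only by implication. The case report form, documentation and data-retention wording in Protocol 4.4.1 is written for subjects who withdraw consent.

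**3. How SAP 8.6 handles the exit.**
- Exit due to a device-related primary safety event: counted as an event.
- Exit due to a non-device-related primary safety event: multiple imputation under missing at random.
- Exit for any other reason, which would include a well-being removal without a primary event: imputed as missing at random.
- The tipping-point analysis is described for the primary endpoint only.

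**4. Which outcomes are exposed.** Permanent morbidity, intracranial hemorrhage, cranial nerve palsy and unresolved neurological deficits are all read at 6 months after the last PHIL treatment. The primary safety outcome closes 30 days after the first procedure, so fewer removals can fall inside its window.

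**5. Sensitivity per subject.**
- With 60 evaluated, one affected subject fewer in the numerator moves the rate by 1/60 = 1.7 points, for example from 5/60 = 8.3% to 4/60 = 6.7%.
- If that subject also leaves the denominator, 5/60 = 8.3% becomes 4/59 = 6.8%, a shift of about 1.6 points.
- The Clopper-Pearson 95% limits for 5/60 are 2.8% to 18.4%. They reflect sampling error and make no allowance for selective loss.

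**6. Range under an assumed number of removals.** Suppose 6 of 75 subjects truly have permanent morbidity: 6/75 = 8.0%, close to the 7.1% and 7.5% that Protocol 7 cites for surgery and Onyx embolization. Suppose also that everyone not removed is evaluated.
- No affected subject removed: 6/75 = 8.0%.
- One removed: 5/74 = 6.8%.
- Two removed: 4/73 = 5.5%.
- Three removed: 3/72 = 4.2%.

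The number removed is an assumption throughout.

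**The case against.** The case on the other side has force, and much of it stands.

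- **Recorded events.** A subject removed because of harm will usually have that harm on record already, and 7.1 requires recorded events to be followed. A reader might infer that all adverse event follow-up stops at removal. The documents do not support that. The gap is clear for new events and for the 6-month mRS. For open events the text is contradictory.
- **Treatment and follow-up.** A reader might infer that stopping PHIL and leaving the study are one act. Protocol 5.8 covers discontinuing PHIL treatment separately and does not link it to study exit.
- **Permanence.** A reader might argue that exit is pointless because the implant is permanent. The documents say that PHIL is implanted and solidifies into an embolus. They do not call it permanent, and the point does not need it.
- **Subjects doing badly leave.** This is a risk, not something that the plan prescribes. Protocol 1.3.3 mentions discontinuation due to adverse events only to set out the investigator's care duty, and SAP 8.6 is a missing-data rule. Neither shows that removals are expected in number. Medical care continues after exit; what lapses is data collection.
- **Sponsor termination.** Section 11.8.4 deals with a different situation, so it is a contrast with 4.4.2 and not a contradiction.
- **SAP safeguards.** SAP 8.6 assigns device-related primary-event exits conservatively and promises sensitivity analysis for missing primary and secondary outcomes. Its description of data not missing at random is worded as an example, so it could be read more widely. However, the later text sends follow-up stopped for any other reason to imputation, and the detailed rules name only the primary endpoints.
- **A halved or doubled rate.** One could set 3/60 = 5.0% against 6/60 = 10.0%. The 10.0% arises only if all 15 losses are unaffected subjects, and the 5.0% only if half of the affected subjects are lost. Neither split has support in the documents.

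**Conclusion.** The gap is real and narrow. A treated subject can be removed on grounds plausibly related to harm. From that point no new adverse events, 6-month mRS or vital status are requested. The 6-month secondary safety outcomes are the ones mainly affected, because they are reported over those evaluated. SAP 8.6 does not close the gap, since a well-being removal would be treated as missing at random unless it followed a device-related primary safety event.

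The size of the bias is unknown because the frequency of removals is not given. The usable figure is about 1.7 points per affected subject lost from the numerator when 60 are evaluated. The direction is also an assumption: removals of subjects doing badly would lower the observed rates, while purely administrative removals of unaffected subjects could raise them. Separately, 7.1 and 7.3 must be reconciled for events still open at exit, whatever the number of removals.

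**What to change.** - **Protocol 4.4 and 4.4.2:** leave the investigator's withdrawal and treatment decisions as they are. Add that removal by the investigator does not end data collection. Unless the subject withdraws consent, collect adverse events, mRS and vital status to 6 months after the last PHIL treatment, by visit, telephone or record review. Protocol 5.12 already gives a precedent for telephone safety follow-up.
- **Protocol 7.1 and 7.3:** end the adverse event window at 6 months after the last PHIL treatment, death or withdrawal of consent. Align 7.3 with it, so that open and new events follow one rule.
- **Recording and reporting:** for every investigator removal, record the reason and the status of open events at exit, and list these removals in the study report.

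The cost is amendment wording and a few extra follow-up contacts at time points already in the schedule.
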